4.2. STUDY ENDPOINTS

4.2.1. Efficacy endpoints

4.2.1.1. Primary efficacy endpoint

- PaO₂/FiO₂ ratio measured at FiO₂ = 1 during mechanical ventilation on ICU admission (time 0) and at 24 hours after ICU admission. Patients on FiO₂ < 1 will be turned back to FiO₂ = 1 for 5 minutes before gas measurement.

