7.5.2. Assessment in the ICU

The following will be assessed during ICU stay and recorded in the CRF, apart from SVR and PVR which will be calculated during data-management. Measurement will be performed as per center practice, unless otherwise specified. For the purpose of this study, clinically diagnosed PGD is defined as:

- An episode of decreased $\text{PaO}_2/\text{FiO}_2$ ratio and chest X-ray results consistent with a PGD score of grade 3, which is not the result of some other secondary cause of graft dysfunction [Christie, 2005]. When diagnosed, the condition is considered clinically recovered for a PGD score of ≤ 1 .
- $\text{PaO}_2/\text{FiO}_2$ ratio. $\text{PaO}_2/\text{FiO}_2$ ratio will be measured at $\text{FiO}_2 = 1$ q24 hours, up to extubation or up to 72 hours after ICU admission, whichever occurs earlier. Patients on $\text{FiO}_2 < 1$ will be turned back to $\text{FiO}_2 = 1$ for 5 minutes before gas measurement. Additional $\text{PaO}_2/\text{FiO}_2$ ratio values obtained as per center standard of care in patients with clinical diagnosis of PGD will be recorded in the CRF up to the clinical recovery of the condition.
- Chest X-rays. A chest X-rays will be obtained 24 hours, 48 hours, and 72 hours after ICU admission (see Appendix 1 for details).
- BP, HR. Vital signs will be measured q12 hours up to ICU discharge or up to 5 days after ICU admission, whichever occurs earlier.
- CO, PA pressure, SVR, PVR, PCWP, CVP. Cardiopulmonary physiologic measurements will be assessed q12 hours when a PA catheter is present, up to ICU discharge or up to 5 days after ICU admission, whichever occurs earlier. Additional measurements obtained as per standard of care in patients with clinical diagnosis of PGD will be recorded in the CRF up to the clinical recovery of the condition.

For all measurements above, the actual date and time of assessment will be recorded in the CRF.

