9.4.2. Primary efficacy analysis

The PaO₂/FiO₂ ratio will be analyzed separately, at the two time points: 0 hours (ICU admission) and 24 hours after ICU admission. Analysis of variance will be used, including terms for treatment and center. The importance of the treatment by center interaction will be investigated but if this is not significant at the 10% level, this term will be excluded from the final model. If a center by treatment interaction is detected, alternative methods of presentation will be explored. Treatment effect will be primarily compared using a one-sided 0.05 level test and then re-tested for consistency with a two-sided 0.05 level test. Type of transplant (single or bilateral) will then be included in the model of the analysis to explore any possible, even unanticipated, differences due to the specific procedure.

Primarily the data will be analyzed excluding missing data. As confirmatory analysis, the ANOVAs will be performed substituting any missing values by the last observation carried forward (LOCF) method, in patients extubated before 24 hours. If the data are missing due to

patient death, the PaO₂/FiO₂ ratio will be given a zero value. If the data are missing due to lack of recording while on mechanical ventilation, these data will not be substituted.

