## 3 STUDY DESIGN

### 3.1 Overview

This is a phase 2, multi-center, randomized, double blind, placebo-controlled, parallel group study of repertaxin in the prevention of PGD after lung transplantation. The study will involve 100

patients undergoing single or bilateral lung transplant who will be randomized to receive either repertaxin or placebo via continuous intravenous (i.v.) infusion administered over 48 hours. Patients randomized into the study who do not go on to receive study drug or lung transplant will be replaced therefore the total number of patients randomized may exceed 100. Patients will be followed for 12 months post-transplant but the majority of study assessments are performed during the intensive care unit (ICU) and hospital stay immediately after surgery.

Patients will be selected for entry into the study from those listed on the center's lung transplant waiting list. Inclusion/exclusion criteria (as listed in protocol sections 5.1 and 5.2), disease history, extrapulmonary site of infection, significant medical history, vital signs, renal and hepatic function, laboratory safety tests and donor information will all be assessed prior to randomization to ensure patient eligibility.

The lung transplant surgery will be performed according to the center's standard practice. The study drug infusion will start approximately 2 hours before the anticipated time of reperfusion of the first allograft. A loading dose will be administered for the first 30 minutes, followed by a maintenance dose for the remaining 47.5 hours of administration.

After completion of surgery, patients will be admitted to an ICU and blood gases ( $\text{PaO}_2$ ,  $\text{FiO}_2$  and  $\text{PaO}_2/\text{FiO}_2$  ratio) will be measured on admission (time 0) and at 24, 48 and 72 hours post ICU admission or until extubation whichever occurs earlier. Chest x-rays, renal and hepatic function and PK sampling will be measured at defined time points within the 72 hours following ICU admission. Vital signs (BP and HR) and cardiopulmonary measurements will be assessed at defined time points within the 5 days post ICU admission or until ICU discharge (or PA catheter removed) whichever occurs earlier. Further patient assessments are made at ICU discharge and hospital discharge.

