### 3.2 Sample Size Considerations

Under the following assumptions:

1. A single primary endpoint –  $\text{PaO}_2/\text{FiO}_2$  ratio
2. One primary comparison: repertaxin versus placebo at 24 hours post ICU admission ( $H_0: \mu_R = \mu_P$ ;  $H_1: \mu_R > \mu_P$ ).
3. A one-sided two group t-test of statistical significance
4.  $\alpha$ -level or probability of Type I error associated with the test of 0.05
5. A placebo mean of 315 mmHg
6. A common standard deviation of 137 mmHg
7. A sample size of 50 in each group

the study has 81% power to detect a difference in means of 70 mmHg ( $\mu_R = 385$  mmHg) and 56% power to detect a difference in means of 50 mmHg ( $\mu_R = 365$  mmHg). The data for assumptions 5 and 6 is taken from the results of 700 lung transplant operations at the Washington University. However, there are currently no data available to provide an estimate of the treatment effect size for this study.

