#### Primary analysis

The ratio at the two time points will be analyzed using a repeated measurements model using PROC MIXED within SAS®. The model will include fixed effect terms for center, time point and treatment. Time point will be specified as a repeated measurement. In order to select an appropriate matrix for the observations within each patient, 3 models will be fitted using the compound symmetry, Huynh-Feldt and unstructured structures. The matrix for the final model will be selected using Akaike's Information Criterion where the lowest value indicates the best fit. Type III sums of squares from the mixed procedure within SAS® will be used to assess the significance of individual terms within the model using the selected matrix structure. The importance of the treatment-by-center interaction will be investigated but if the term is not significant at the 10% level, it will be excluded from subsequent models. If there are insufficient data within each center and treatment combination to allow estimation of effects, centers will be pooled based on similar surgical practices.

The adjusted least squares means will be estimated for each combination of time point and treatment. The treatment effect within each time point will be compared using a one sided test at the 5% level. Missing data will be excluded. The primary analysis will be performed for the ITT population.

The tests of the fixed effects will be presented, together with the estimated least squares means and summary statistics of the raw PaO2/FiO2 ratio for each of the two treatments at each time point. The estimated treatment difference between repertaxin and placebo at each time point will be presented together with the corresponding 95% confidence interval. The confidence interval will be generated using  $\alpha=0.10$  and the lower limit will be replaced by  $-\infty$ .

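### The SAP's primary model has no treatment-by-time term, so the 24-hour effect it reports is a blend with ICU admission, and excluded 24-hour values weaken it further

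*SAP*

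**What the plan says.** **When the ratio exists.** Protocol 4.2.1.1 defines the primary endpoint as the ratio measured "during mechanical ventilation on ICU admission (time 0) and at 24 hours after ICU admission". Protocol 7.5.2 schedules it "q24 hours, up to extubation or up to 72 hours after ICU admission, whichever occurs earlier", and SAP 3.1 agrees: "24, 48 and 72 hours post ICU admission or until extubation whichever occurs earlier". A patient extubated or dead before 24 hours therefore has no 24-hour value.

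**What is powered.** SAP 3.2 assumes "One primary comparison: repertaxin versus placebo at 24 hours post ICU admission", with 50 patients per group.

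**How it is analyzed.** Protocol 9.4.2 says the ratio "will be analyzed separately, at the two time points", by ANOVA, and "Primarily the data will be analyzed excluding missing data". SAP 9.5.1 replaces this with one repeated-measures model for both times: "The model will include fixed effect terms for center, time point and treatment". The only interaction named there is treatment-by-center, and the shell for Tables 2.1.x and 2.2.x in SAP 13 has rows for center, time, treatment and center-by-treatment. Yet SAP 9.5.1 also wants least squares means for every time-by-treatment cell and a one-sided test of treatment within each time, and the shell has separate difference rows for 0 and 24 hours. On missing values it says: "Missing data will be excluded. The primary analysis will be performed for the ITT population".

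**The planned check.** One repeat of the primary analysis carries the last value forward for patients extubated within 24 hours and assigns zero to those who died. Ratios missing for other reasons are not substituted.

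**The concern.** With time and treatment entered only as main effects, the model holds a single treatment parameter. The 0-hour and 24-hour rows of the shell would show the same difference, standard error and p-value. That figure is a weighted mean of the effects at the two times, not the 24-hour effect on which the trial is powered.

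Missing values make this worse. The mixed model normally drops only the missing 24-hour record and keeps the patient's admission value, and in the model as listed that value feeds the shared difference. The more patients leave before 24 hours, the more the figure reported for 24 hours reflects admission. Leaving is also an outcome in its own right: extubation and death come after randomization and treatment may affect both.

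Protocol 9.1 justifies a possibly underpowered study by the information it will give on the effect size in the primary variable. That effect size is what becomes hard to read.

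**Working it through.** **1. The plan's own figure.** SAP 3.2: n = 50 per group, SD 137, one-sided 0.05. SE = 137 × √(2/50) = 27.4. For 70 mmHg the noncentrality is 70/27.4 = 2.55, and the noncentral t gives 81.4% (stated 81%). For 50 mmHg it gives 56.6% (stated 56%). Both figures assume that all 100 patients have a 24-hour value and that the contrast belongs to 24 hours alone.

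**2. Listed terms, complete data.** Inputs: σ0 = 137 and σ1 = 117 (Protocol 9.1); correlation ρ = 0.5 (assumed); effect 0 at admission and 70 mmHg at 24 hours (assumed). Center is left out, since treatment is balanced within centers. The weight that generalized least squares gives to the 24-hour effect is

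w24 = (σ0² − ρσ0σ1) / (σ0² + σ1² − 2ρσ0σ1) = (18769 − 8014.5) / (18769 + 13689 − 16029) = 10754.5/16429 = 0.655.

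Shared difference = 0.655 × 70 = **45.8 mmHg**, printed in both rows. With ρ from 0.3 to 0.7 it is 42.8 to 52.7. Under compound symmetry with equal SDs, one of the three structures the SAP may select, it is 35.0.

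**3. Listed terms, share m of 24-hour values missing at random.** The information per arm is I = (1 − m)V⁻¹ + m·diag(1/σ0², 0), and w24 = (I01 + I11)/(I00 + 2·I01 + I11). In units of 10⁻⁵, V⁻¹ has entries 7.104, −4.159 and 9.740, and 1/σ0² = 5.328. For m = 0.3:

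- I00 = 0.7 × 7.104 + 0.3 × 5.328 = 6.571
- I01 = −2.911
- I11 = 6.818
- w24 = 3.907/7.567 = 0.516, so the shared difference is **36.1 mmHg**.

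For m = 0.2 it is 39.6. The error can also run the other way: with 70 mmHg at admission and nothing at 24 hours, the 24-hour row would show 24.2 mmHg (complete data) or 33.9 mmHg (30% missing).

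**4. With the term added.** Large-sample simulation, true 24-hour effect 70 mmHg, ρ = 0.5. Assumed: 30% of placebo patients extubated and 2% dead before 24 hours, with better oxygenation leading to earlier extubation. Estimates in mmHg:

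| Leaving depends on | Admission effect | Observed 24 h values only | Model with treatment-by-time, unstructured | LOCF/zero |
|---|---|---|---|---|
| 24 h state | 70 | 48.4 | 52.3 | 71.8 |
| 24 h state | 0 | 48.5 | 52.5 | 39.8 |
| Time 0 ratio only | 70 | 61.0 | 70.3 | 76.7 |
| Time 0 ratio only | 0 | 70.0 | 69.9 | 47.6 |

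With no drug effect at either time and the same rule for leaving in both arms, all three are about 0. The model with the term recovers 70 when leaving depends only on time 0, and falls short when it depends on the unseen 24-hour state. LOCF/zero lands on either side of 70 according to the admission effect, so it is not a bound.

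**The case against.** The strongest reply is that the missing term is a drafting slip. SAP 9.5.1 asks for cell means and an effect within each time, the shell has two difference rows, and nobody would knowingly print the same number twice. That is probably right, and it means the figures in steps 2 and 3 describe the SAP run to the letter, not necessarily what the sponsor intends. But the model statement and the fixed-effects shell agree in leaving the term out, and this is the text that will be programmed and validated against. The correction should be written down.

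The second reply is that the plan foresaw extubation and death by name, and that the 24-hour PGD score and time to freedom from ventilation give further views. This stands in part. The PGD score can grade extubated patients through the nasal-cannula rule in Protocol Appendix 1, though the SAP's definition does not repeat it. The ventilation analysis credits early extubation but censors deaths. Neither yields a 24-hour effect in mmHg.

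A reader might infer three stronger things that the documents do not support:

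- *That early leavers drop out of the SAP's primary analysis altogether.* This is true of the t-test used for power and of the protocol's separate 24-hour ANOVA. In the SAP's mixed model only the 24-hour record is lost.
- *That the 24-hour result is known to be biased, and in which direction.* Step 4 shows no bias when extubation depends only on the admission ratio and the model terms.
- *That true power is a particular figure below 81%.* No extubation rate, early death rate or within-patient correlation is given, and weaning follows center practice.

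**Conclusion.** The concern holds in two parts of unequal strength.

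**The model as written is wrong for its purpose.** This needs no assumption about missing data: the listed terms cannot produce separate effects at 0 and 24 hours. How far the shared figure departs from the 24-hour effect depends on the admission effect. It is 46 rather than 70 mmHg if there is none (complete data, ρ = 0.5), and there is no departure with complete data if the effects are equal at both times.

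**The missing 24-hour values are outcome-related, and one planned repeat cannot settle their influence.** With the term in place, the 24-hour contrast is unbiased for extubation if leaving depends only on the time 0 ratio and the model terms, with the covariance adequately modelled. It can be biased if leaving follows the unseen 24-hour state, and for deaths no 24-hour ratio exists to be estimated. The 52 mmHg in step 4 is an illustration under assumed rates. The study is described as not pivotal, so this is a correction worth making before lock, not a threat to the trial.

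**What to change.** In the SAP, before Month 1 database lock:

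1. **Add treatment-by-time** to the model in SAP 9.5.1 and to the fixed-effects shell for Tables 2.1.x and 2.2.x, and take the treatment contrast at each time from that model. This restores what Protocol 9.4.2 specifies. The price is precision when the effect is the same at both times. With complete data the standard error of the 24-hour contrast is 117 × √(2/50) = 23.4 mmHg, against 21.7 for the shared contrast. With 20–40% of placebo patients assumed extubated by 24 hours and 70 mmHg at both times, simulated power was 57–81% with the term and 85–91% without it.
2. **Show the missingness.** In Tables 2.1.x and 2.2.x give, by arm and time, the numbers measured, extubated, dead and not recorded while ventilated. Describe the mmHg result as the ratio in patients still ventilated. Count a ratio within the Appendix 6 window as measured, so that the categories do not overlap.

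The LOCF/zero repeat stays as planned. A supportive ranked analysis of all patients, with death worst and extubation best, is optional. It gives no mmHg estimate and brings in local weaning practice. If used, it must define status at 24 hours without reference to later reintubation, and say whether an in-window ratio takes precedence over an extubation shortly afterwards.

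The cost is a line of model text, a few shell rows and entries in SAP 1.2 and 1.3; SAP 1.2 currently reports no change from the protocol. No protocol amendment is needed. Maintained extubation and death are already recorded. An extubation that failed before 24 hours is not a required record (Protocol 7.5.3), so a few patients may need a site query to be classified.

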### 13 TABLE SHELLS

Tables 2.1.x and 2.2.x Repeated Measurements Analysis

Tests of Fixed Effects				
Source	NDF	DDF	Type III F	P
Center	x	x	x.xx	0.xxxx
Time	x	x	x.xx	0.xxxx
Treatment	x	x	x.xx	0.xxxx
Center-by-treatment	x	x	x.xx	0.xxxx

Summary Statistics			
		Repertaxin	Placebo
Time=0	Least Squares Mean	xx.xx	xx.xx
	Mean	xx.xx	xx.xx
	SD	xx.xx	xx.xx
	Median	xx.xx	xx.xx
	Range	(xx.x; xx.x)	(xx.x; xx.x)
	N	x	x
Time=24	Least Squares Mean	xx.xx	xx.xx
	Mean	xx.xx	xx.xx
	SD	xx.xx	xx.xx
	Median	xx.xx	xx.xx
	Range	(xx.x; xx.x)	(xx.x; xx.x)
	N	x	x

Treatment Comparison					
Time	Comparison	Difference between Means	SE of difference	95% confidence interval	P-value
0	Repertaxin - Placebo	x.xxx	x.xxx	(-x.xx, x.xx)	0.xxxx
24	Repertaxin - Placebo	x.xxx	x.xxx	(-x.xx, x.xx)	0.xxxx

Table 2.3.x Analysis of PGD Score

	Repertaxin		Placebo		Odds Ratio [1]	95% CI for Odds Ratio	P-value [2]
	N	%	N	%			
Grade 0	xx	xx	xx	xx	x.xx	(x.xx, x.xx)	0.xxx
Grade 1	xx	xx	xx	xx			
Grade 2	xx	xx	xx	xx			
Grade 3	xx	xx	xx	xx			

[1] Odds ratio is Repertaxin:Placebo

[2] The p-value is obtained from a Cochran-Mantel-Haenszel test of the treatment difference.

Table 2.4.x Time to Freedom from Mechanical Ventilation

TIME POINT	Repertaxin				Placebo				Difference in Event Prob.	95% CI for Difference
	N=	Number of Patients Remaining	Cumulative Number of Events	Event Probability S.E.	N=	Number of Patients Remaining	Cumulative Number of Events	Event Probability S.E.		
24 hrs										
48 hrs										
72 hrs										
96 hrs										
etc										
Censored (N)	xx				xx				Chi-sq statistic	P-value
Log-rank										

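### The one-sided 95% interval for the primary endpoint keeps the wrong limit, so it includes zero whenever the primary test shows benefit

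*SAP*

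**What the plan says.** SAP 3.2 sets the alternative as a repertaxin mean above the placebo mean and lists "A one-sided two group t-test of statistical significance" with a Type I error of 0.05. SAP 9.5.1 carries this into the analysis: "The treatment effect within each time point will be compared using a one sided test at the 5% level". Protocol 9.4.2 agrees: "Treatment effect will be primarily compared using a one-sided 0.05 level test", followed by a two-sided test for consistency.

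For estimation, SAP 9.5.1 states that the treatment difference at each time point "will be presented together with the corresponding 95% confidence interval". It specifies the construction: alpha = 0.10, "and the lower limit will be replaced by" minus infinity.

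The shell for Tables 2.1.x and 2.2.x (SAP 13) defines the comparison as repertaxin minus placebo and shows an interval with two finite limits.

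**The concern.** A higher ratio is better and the contrast is repertaxin minus placebo, so evidence of benefit lies in the lower confidence limit: how small could the difference plausibly be? The SAP discards that limit and keeps the upper one, which answers whether repertaxin could be worse than placebo by a significant margin. That is not the question the primary test asks.

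Two things are at stake. First, a reader of the primary table would see a significant p-value beside an interval that includes no effect and would reasonably conclude that one of them is wrong. Second, both documents say that no data exist to estimate the effect size, and Protocol 9.1 justifies the trial, even if underpowered, partly by what it will show about that effect. A lower bound on the benefit is the most useful thing the interval could provide, and it is the limit removed.

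The planned quality control would not catch this. SAP 10 relies on independent programming and on outputs agreeing with the plan, so two programmers following the same sentence would produce the same wrong interval.

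**Working it through.** **Inputs**

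- Alternative: repertaxin mean greater than placebo mean (SAP 3.2, second assumption).
- Test: one-sided, 0.05, at each time point (SAP 9.5.1).
- Contrast: repertaxin minus placebo (SAP 13, shell for Tables 2.1.x and 2.2.x).
- "A placebo mean of 315 mmHg"; "A common standard deviation of 137 mmHg"; 50 patients per group (SAP 3.2).

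**Step 1: reproduce the stated power.** SE = 137 × √(2/50) = 27.4 mmHg. The critical value is t(0.95, 98) = 1.6606. From the noncentral t with 98 df:

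| True difference | Power, one-sided 0.05 | SAP states |
|---|---|---|
| 70 mmHg | 81.4% | 81% |
| 50 mmHg | 56.6% | 56% |

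A two-sided 0.05 test would give about 72.4% and 44.6% (normal approximation), so the power statement is for the one-sided test for benefit.

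**Step 2: the two candidate intervals.** Write d for the observed difference, L = d − 1.6606 × SE and U = d + 1.6606 × SE. The half-width is 1.6606 × 27.4 = 45.5 mmHg. Using alpha = 0.10 is correct, because each limit of a two-sided 90% interval is a one-sided 95% limit. Only the choice of limit to drop is in question.

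| Observed d | t = d/SE | One-sided p | Matching interval (L, +∞) | SAP interval (−∞, U) |
|---|---|---|---|---|
| 70 | 2.555 | 0.006 | (24.5, +∞) | (−∞, 115.5) |
| 50 | 1.825 | 0.036 | (4.5, +∞) | (−∞, 95.5) |

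Both matching intervals exclude zero, in line with the p-values. Both SAP intervals include it.

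**Step 3: the general argument.** The test is significant for benefit only if d > t × SE. Then U = d + t × SE > 2 × t × SE > 0. So zero lies inside (−∞, U) for every significant result, whatever the SE, degrees of freedom or covariance structure. With the planning inputs, significance needs d > 45.5 mmHg, so U > 91.0 mmHg. The SAP interval can exclude zero only when d < −t × SE, that is, when repertaxin is significantly worse.

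**Step 4: simulation check.** With 400,000 simulated trials at each true difference of 0, 50 and 70 mmHg, the SAP interval contained zero in 100% of the significant trials. The interval (L, +∞) excluded zero exactly when the test was significant, with no disagreements.

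**Step 5: reach.** SAP 9.5.1 repeats the primary analysis in its one-sided sensitivity analyses, and SAP 9.5.2.1 analyses 48 and 72 hours in the same way as the primary analysis. The instruction therefore carries to Tables 2.1.1, 2.1.2, 2.1.4 to 2.1.6 and 2.2.1 to 2.2.4.

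**The case against.** The strongest reply is that this is a reporting error that cannot change whether the trial succeeds. The primary comparison is the one-sided test, and no decision rule uses the interval. The point estimate, SE, p-value, Type I error and power are all untouched. Protocol 9.4.2 does not ask for an interval, and SAP 9.5.1 itself says the study is not pivotal. The shell prints the difference and its SE, so a reader could rebuild an approximate lower limit, and the two-sided Table 2.1.3 would presumably show a finite one. The shell is shared with Table 2.1.3, where two finite limits are appropriate. Strictly, an upper bound above zero is also not logically incompatible with a significant test for benefit; it answers a different question.

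These points are fair and limit the damage, but they do not make the specified interval correct. The SAP calls it the interval corresponding to the estimated difference and places it beside the one-sided p-value. It does not say how the interval in Table 2.1.3 is built. The shared shell does not show the layout the text prescribes for the one-sided tables.

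The mmHg figures are also only illustrative. They use a simple t-test with 50 analysed per arm, whereas the planned analysis is a repeated-measures model with center that excludes missing data. Protocol 9.1 gives an SD of 117 at 24 hours; that yields SE = 117 × √(2/50) = 23.4 and a threshold of 1.6606 × 23.4 = 38.9 mmHg instead of 45.5. The sign argument does not depend on any of these values.

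**Conclusion.** The concern holds. The interval in SAP 9.5.1 is cut on the wrong side for the stated alternative and contrast, and nothing elsewhere in either document corrects it. Whenever the primary test shows benefit, the reported interval will include zero; this is certain for any standard error. With the planning SD and 50 per arm, a 70 mmHg difference would be printed as (−∞, 115.5) when the matching interval is (24.5, +∞).

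The conclusion rests on the direction of the alternative in SAP 3.2 and the sign of the contrast in SAP 13. A lower limit of minus infinity would suit a placebo-minus-repertaxin contrast, but the shell fixes the reverse. It should be corrected before lock because it sits in the headline result and would mislead exactly when the trial succeeds.

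**What to change.** In SAP 9.5.1, keep alpha = 0.10 and state that the **upper** limit is replaced by +∞, so that the one-sided 95% interval is (L, +∞). Change the shell for the one-sided tables (2.1.1, 2.1.2, 2.1.4 to 2.1.6 and 2.2.1 to 2.2.4) to show that layout, and state that Table 2.1.3 carries a two-sided 95% interval with two finite limits.

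An acceptable alternative is to report the two-sided 90% interval with both limits in the one-sided tables. The 95% label in the text and shell must then be changed to 90% for those tables.

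The cost is one sentence and a shell edit, with no effect on data, power or the test. SAP 1.1 says the plan is finalized before database lock, so the change can still be pre-specified. Made after unblinding, it would look driven by the data.
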